#### 6.6.1.1. All adverse events

Adverse events will be summarized by worst severity (according to NCI-CTCAE version 4.03) per patient, using the latest version of MedDRA preferred term (PT) as event category and MedDRA primary system organ class (SOC) body term as Body System category.

In case a patient has events with missing and non-missing grades, the maximum of the non-missing grades will be displayed. No imputation of missing grades will be performed.

The following tables will be created:

- The overall summary of AEs table will include the frequency (number and percentage) of patients with each of the following by treatment group:
  - TEAEs
  - TEAEs, Grade  $\geq 3$
  - Related TEAEs
  - Related TEAEs, Grade  $\geq 3$
  - TEAEs leading to interruption of any study drug
  - TEAEs leading to discontinuation of avelumab

- TEAEs leading to discontinuation of utomilumab
- TEAEs leading to discontinuation of PF-04518600
- TEAEs leading to discontinuation of PD 0360324
- TEAEs leading to discontinuation of CMP-001
- TEAEs leading to discontinuation of any study drug
- Related TEAEs leading to discontinuation of avelumab
- Related TEAEs leading to discontinuation of utomilumab
- Related TEAEs leading to discontinuation of PF-04518600
- Related TEAEs leading to discontinuation of PD 0360324
- Related TEAEs leading to discontinuation of CMP-001
- Related TEAEs leading to discontinuation of any study drug
- Serious TEAEs
- Related Serious TEAEs
- TEAEs leading to death
- Related TEAEs leading to death
- irAEs
- IRRs
- Cytokine Release Syndrome (Combination F only)
- TEAEs by SOC and PT and worst grade
- TEAEs related to any study drug by SOC and PT and worst grade
- TEAEs leading to death by SOC and PT
- Related TEAEs leading to death by SOC and PT

#### **6.6.1.2. Adverse events leading to interruption of study treatment**

The eCRF does not allow for a clear separation between interruption of an infusion and delays of administration for a parenteral drug as both are recorded using the same term on the eCRF (“Drug interrupted”). IRRs will be excluded in the analysis of AEs leading to Drug Interruption in case they only led to an interruption of the infusion (ie, did not lead to a dose reduction or a dose delay).

As such, AEs leading to interruption will be defined as AEs identified in the AE eCRF page with an action taken with study treatment of ‘drug interrupted’ excluding

- IRRs that occurred on the day of infusion with  $\geq 90\%$  of the planned dose given (ie IRRs that did not lead to a dose reduction) and subsequent administration of study drug had no delay (as defined in Section 6.5.3.6). These IRRs will be considered as IRRs leading to interruption of infusion.
- IRRs occurring on the day after infusion and subsequent dose administration had no delay (as defined in Section 6.5.3.6).

The frequency (number and percentage) of patients with each of the following will be presented for TEAEs leading to interruption of each study drug by treatment group:

- TEAEs leading to interruption of avelumab by SOC and PT
- TEAEs leading to interruption of utomilumab by SOC and PT
- TEAEs leading to interruption of PF-04518600 by SOC and PT
- TEAEs leading to interruption of PD 0360324 by SOC and PT

The listing of all AEs leading to interruption of study treatment will also be provided with the relevant information.

#### **6.6.1.3. Adverse events leading to discontinuation of study treatment**

The frequency (number and percentage) of patients with each of the following will be presented for TEAEs leading to permanent discontinuation of each study drug and study treatment, by treatment group:

- TEAEs leading to discontinuation of avelumab by SOC and PT
- TEAEs leading to discontinuation of utomilumab by SOC and PT
- TEAEs leading to discontinuation of PF-04518600 by SOC and PT
- TEAEs leading to discontinuation of PD 0360324 by SOC and PT
- TEAEs leading to discontinuation of CMP-001 by SOC and PT
- TEAEs leading to discontinuation of any study drug by SOC and PT
- Related TEAEs leading to discontinuation of avelumab by SOC and PT
- Related TEAEs leading to discontinuation of utomilumab by SOC and PT
- Related TEAEs leading to discontinuation of PF-04518600 by SOC and PT
- Related TEAEs leading to discontinuation of PD 0360324 by SOC and PT
- Related TEAEs leading to discontinuation of CMP-001 by SOC and PT
- Related TEAEs leading to discontinuation of any study drug by SOC and PT

The listing of all AEs leading to treatment discontinuation will also be provided with the relevant information.

### **6.6.2. Deaths**

The frequency (number and percentage) of patients in the safety analysis set who died and who died within 30 days after last dose of study treatment as well as the reason for death, will be tabulated based on information from the ‘Notice of Death’ and ‘Survival Follow-Up’ eCRFs, by treatment group.

- All deaths
- Deaths within 30 days after last dose of study treatment
- Reason for Death
  - Disease progression
  - Study treatment toxicity
  - AE not related to study treatment
  - Unknown
  - Other.

In addition, date and cause of death will be provided in individual patient data listing together with selected dosing information (study treatment received, date of first / last administration, dose) and will include the following information:

- AEs with fatal outcome (list preferred terms of AEs with outcome=Fatal, as well as AEs of Grade 5),
- Flag for death within 30 days of last dose of study treatment.

### **6.6.3. Serious adverse events**

The frequency (number and percentage) of patients with each of the following will be presented for treatment-emergent SAEs by treatment group:

- SAEs by SOC and PT
- Related SAEs by SOC and PT

The listings of all SAEs will also be provided with the relevant information with a flag for SAEs with onset outside of the on-treatment period.

### **6.6.4. Other significant adverse events**

The frequency (number and percentage) of patients with each of the following will be presented for irAEs, by treatment group:

- irAEs, by Cluster, PT, and maximum CTCAE Grade
- irAEs leading to discontinuation of avelumab, by Cluster and PT
- irAEs leading to discontinuation of any study drug by Cluster and PT
- Serious irAEs, by Cluster and PT

The listing of all irAEs will also be provided with the relevant information with a flag for irAEs with onset outside of the on-treatment period.

The frequency (number and percentage) of patients with each of the following will be presented for IRRs, by treatment group and for each study drug:

- IRRs, by PT and maximum CTCAE grade
- IRRs leading to discontinuation of avelumab, by PT
- IRRs leading to discontinuation of any study drug, by PT
- Serious IRRs, by PT
- Time related to first onset of an IRR (infusion 1, infusion 2, infusion 3, infusion 4 or later). For IV study drugs administered in combination the infusion numbers are those associated with the regimen, rather than the individual study drugs.

The listing of all IRRs will also be provided with the relevant information with a flag for IRRs with onset outside of the on-treatment period.

For Combination F only (Cohorts F1, F2 and F3) Cytokine Release Syndrome (as defined in the SRP) may be summarized and listed as described above for irAEs by Cluster and PT or by PT only, as applicable.

### **6.6.5. Laboratory data**

#### **6.6.5.1. Hematology and chemistry parameters**

Laboratory results will be classified according to the NCI-CTCAE criteria version 4.03. Non-numerical qualifiers (with the exception of fasting flags) will not be taken into consideration in the derivation of CTCAE criteria (eg, hypokalemia Grade 1 and Grade 2 are only distinguished by a non-numerical qualifier and therefore Grade 2 will not be derived). Additional laboratory results that are not part of NCI-CTCAE will be presented according to the categories: below normal limit, within normal limits and above normal limit (according to the laboratory normal ranges).

Abnormalities classified according to NCI-CTCAE toxicity grading v.4.03 will be described using the worst grade. For those parameters which are graded with two toxicities such as potassium (hypokalemia/hyperkalemia), the toxicities will be summarized separately. Low direction toxicity (eg, hypokalemia) grades at baseline and post baseline will be set to 0 when the variables are derived for summarizing high direction toxicity (eg, hyperkalemia), and vice versa.

For **WBC differential counts** (total neutrophil [including bands], lymphocyte, monocyte, eosinophil, and basophil counts), the absolute value will be used when reported. When only percentages are available (this is mainly important for neutrophils and lymphocytes, because the CTCAE grading is based on the absolute counts), the absolute value is derived as follows:

$$\text{Derived differential absolute count} = (\text{WBC count}) \times (\text{Differential \%value} / 100)$$

If the range for the differential absolute count is not available (only range for value in % is available) then Grade 1 will be attributed to as follows:

- Lymphocyte count decreased:
  - derived absolute count does not meet Grade 2-4 criteria, and
  - % value < % LLN value, and
  - derived absolute count  $\geq 800/\text{mm}^3$
- Neutrophil count decreased
  - derived absolute count does not meet Grade 2-4 criteria, and
  - % value < % LLN value, and
  - derived absolute count  $\geq 1500/\text{mm}^3$

For **calcium**, CTCAE grading is based on Corrected Calcium and Ionized Calcium (CALCIO). Corrected Calcium is calculated from Albumin and Calcium as follows

Corrected calcium (mmol/L) = measured total Calcium (mmol/L) + 0.02 (40 - serum albumin [g/L])

**Liver function tests:** Alanine aminotransferase (ALT), aspartate aminotransferase (AST), and total bilirubin (TBILI) are used to assess possible drug induced liver toxicity. The ratios of test result over upper limit of normal (ULN) will be calculated and classified for these three parameters during the on-treatment period.

Summary of liver function tests will include the following categories. The number and percentage of patients with each of the following during the on-treatment period will be summarized by treatment group:

- $\text{ALT} \geq 3 \times \text{ULN}$ ,  $\text{ALT} \geq 5 \times \text{ULN}$ ,  $\text{ALT} \geq 10 \times \text{ULN}$ ,  $\text{ALT} \geq 20 \times \text{ULN}$
- $\text{AST} \geq 3 \times \text{ULN}$ ,  $\text{AST} \geq 5 \times \text{ULN}$ ,  $\text{AST} \geq 10 \times \text{ULN}$ ,  $\text{AST} \geq 20 \times \text{ULN}$
- $(\text{ALT or AST}) \geq 3 \times \text{ULN}$ ,  $(\text{ALT or AST}) \geq 5 \times \text{ULN}$ ,  $(\text{ALT or AST}) \geq 10 \times \text{ULN}$ ,  $(\text{ALT or AST}) \geq 20 \times \text{ULN}$
- $\text{TBILI} \geq 2 \times \text{ULN}$
- Concurrent  $\text{ALT} \geq 3 \times \text{ULN}$  and  $\text{TBILI} \geq 2 \times \text{ULN}$
- Concurrent  $\text{AST} \geq 3 \times \text{ULN}$  and  $\text{TBILI} \geq 2 \times \text{ULN}$
- Concurrent  $(\text{ALT or AST}) \geq 3 \times \text{ULN}$  and  $\text{TBILI} \geq 2 \times \text{ULN}$
- Concurrent  $(\text{ALT or AST}) \geq 3 \times \text{ULN}$  and  $\text{TBILI} \geq 2 \times \text{ULN}$  and  $\text{ALP} > 2 \times \text{ULN}$
- Concurrent  $(\text{ALT or AST}) \geq 3 \times \text{ULN}$  and  $\text{TBILI} \geq 2 \times \text{ULN}$  and  $(\text{ALP} \leq 2 \times \text{ULN}$  or missing)

Concurrent measurements are those occurring on the same date.

Categories will be cumulative, ie, a patient with an elevation of AST  $\geq 10 \times \text{ULN}$  will also appear in the categories  $\geq 5 \times \text{ULN}$  and  $\geq 3 \times \text{ULN}$ . Liver function elevation and possible Hy's Law cases will be summarized using frequency counts and percentages.

An evaluation of Drug-Induced Serious Hepatotoxicity (eDISH) plot will also be created, with different symbols for different treatment groups, by graphically displaying

- peak serum ALT(/ULN) vs peak total bilirubin (/ULN) including reference lines at ALT=3×ULN and total bilirubin =2×ULN.
- peak serum AST(/ULN) vs peak total bilirubin (/ULN) including reference lines at AST=3×ULN and total bilirubin =2×ULN .

In addition, a listing of all TBILI, ALT, AST and ALP values for patients with concurrent (ALT or AST)  $\geq 3 \times \text{ULN}$  and TBILI  $\geq 2 \times \text{ULN}$  and (ALP  $\leq 2 \times \text{ULN}$  or missing) will be provided.

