**Important for Combination F:** CMP-001 activates pDCs through agonism of TLR9. Upon activation by CMP-001, pDCs will induce large amounts of IFN $\alpha$  and Th1-promoting cytokines. Therefore, it is expected that toxicities associated with CMP-001 dosing may resemble interferon-related toxicities and symptoms associated with cytokine release, such as fever, flu-like symptoms, tachypnea, headache, tachycardia, hypotension, rash, and hypoxia which may present hours after CMP-001 injection. Therefore, AEs such as headache, fever, flu-like symptoms and/or hypotension that are  $\leq$  Grade 3 AND resolved to  $\leq$  Grade 1 within 24 hours with standard supportive care will not be considered as DLTs.

- Non-hematologic Grade  $\geq 3$  laboratory abnormality if medical intervention is required to treat the patient or the abnormality leads to hospitalization.
  - Single laboratory values out of normal range that are unlikely related to trial treatment according to the Investigator, do not have any clinical correlate, and resolve to Grade  $\leq 1$  within 7 days with adequate medical management are not to be considered DLTs;
  - ALT or AST  $> 3$  x upper limit of normal (ULN) (if normal at baseline) or  $> 3$  x ULN and doubling the baseline (if  $> ULN$  at baseline) associated with bilirubin  $> 2$  x ULN.

Non-Adherence to Treatment Schedule:

- Delay of  $\geq 3$  weeks in receiving the next scheduled administration due to persisting treatment-related toxicities;
- Failure to receive at least 75% of the planned doses each of the investigational products during the DLT observation period due to treatment-related toxicities.

In the absence of associated clinical abnormalities, abnormal laboratory tests should be repeated to confirm relevance.

While the rules for adjudicating DLTs in the context of the dose determination phase (Phase 1b) are specified above, an AE not listed above, or an AE meeting the DLT criteria above but occurring outside of the DLT observation period may be defined as a DLT after consultation between Sponsor and Investigator, based on the emerging safety profile.

- Phase 2: Confirmed objective response (OR), as assessed by the Investigator using RECIST v1.1.

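### Same-date rule in SAP 6.6.5.1 leaves some patients in the eDISH upper-right quadrant but out of every combined liver row and the dedicated listing

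*SAP*

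**What the plan says.** The liver function part of SAP Section 6.6.5.1 has five combined categories. Each pairs ALT, AST, or either one, at 3×ULN or more with TBILI at 2×ULN or more, and two of them add a condition on ALP. All five are labelled concurrent, and "Concurrent measurements are those occurring on the same date". The section also promises that "Liver function elevation and possible Hy's Law cases will be summarized using frequency counts and percentages", and gives no other definition of a possible case.

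The eDISH plots are specified as "peak serum ALT(/ULN) vs peak total bilirubin (/ULN) including reference lines at ALT=3×ULN and total bilirubin =2×ULN" and "peak serum AST(/ULN) vs peak total bilirubin (/ULN) including reference lines at AST=3×ULN and total bilirubin =2×ULN". They carry no same-date condition.

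The patient-level follow-up is described as "In addition, a listing of all TBILI, ALT, AST and ALP values for patients with concurrent (ALT or AST"), at the same thresholds and with ALP at most 2×ULN or missing.

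Section 6.6.5.2 separately provides listings of all laboratory results by patient and date, with out-of-range values flagged. It applies no selection for combined elevations.

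**The concern.** One section uses two definitions at the same thresholds, and no output connects them. The plot takes in any patient whose two peaks cross the lines. The table and listing take in only patients with one date on which both lines are crossed. Bilirubin can reach 2×ULN after the transaminase has fallen below 3×ULN, or the two samples can be drawn a day apart. Such a patient is a point in the quadrant while the combined rows show nothing and the listing does not contain the patient.

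A reader who sees the point cannot find the patient without searching the full laboratory listing. Several Phase 2 cohorts are planned at 20 to 35 patients, so one patient is 1/35 = 2.9% to 1/20 = 5% of a cohort. A single unresolved point is then visible in the report and worth explaining.

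**Working it through.** The plan gives no figure to reproduce. The check has two parts.

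**1. The rules applied literally to hypothetical patients.** Values are multiples of ULN. AST is assumed below 3 throughout. ALP is at most 2 except in patient E.

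| Patient | Values | eDISH quadrant | Combined row | Dedicated listing |
|---|---|---|---|---|
| A | Day 15: ALT 6, TBILI 0.9. Day 29: ALT 4, TBILI 2.4 | yes | yes | yes |
| B | Day 15: ALT 6, TBILI 0.9. Day 29: ALT 2.4, TBILI 2.6 | yes | no | no |
| C | Day 15: ALT 6 only. Day 16: TBILI 2.5 only | yes | no | no |
| D | Day 15: ALT 6, TBILI 0.9. Day 215: ALT 1, TBILI 2.5 | yes | no | no |
| E | One date: ALT 6, TBILI 2.5, ALP 3 | yes | yes | no |

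B and C show the gap. A shows that a later bilirubin rise is still captured when ALT is at 3×ULN or more on that date. D shows that the quadrant also collects elevations that are probably unrelated. E is left out of the listing by the ALP condition, not by the date rule.

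Replacing the same date with a window (TBILI threshold met within w days after the ALT threshold) gives:
- w = 0 or 7 days: B is missed.
- w = 14, 28 or 30 days: B is caught.
- C is missed at w = 0 and caught from w = 7.
- D stays out at every one of these windows.

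**2. An illustrative size.** The SAP contains no laboratory schedule, so every input is an assumption:
- L = days that ALT/AST stays at 3×ULN or more;
- k = days from that crossing until TBILI reaches 2×ULN (k < L), after which TBILI stays up long enough to be sampled;
- s = days between draws, at random phase. The value s = 14 is borrowed from the two-weekly dosing and s = 28 from the cycle length.

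Then:
- P(transaminase rise sampled, so patient in quadrant) = min(1, L/s)
- P(counted by the same-date rule) = min(1, (L−k)/s)
- share of quadrant patients missed = 1 − P(counted)/P(in quadrant)

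| L | k | s | In quadrant | Counted | Missed among those in quadrant |
|---|---|---|---|---|---|
| 14 | 3 | 14 | 14/14 = 100% | 11/14 = 79% | 21% |
| 14 | 7 | 14 | 14/14 = 100% | 7/14 = 50% | 50% |
| 10 | 7 | 14 | 10/14 = 71% | 3/14 = 21% | 1 − 3/10 = 70% |
| 21 | 7 | 28 | 21/28 = 75% | 14/28 = 50% | 1 − 14/21 = 33% |
| 21 | 7 | 14 | 100% | 14/14 = 100% | none |

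The denominator must be patients whose transaminase rise was sampled. A rise that falls between draws is absent from the plot as well, and no change to the table would recover it.

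**The case against.** The best defence is that nothing is mislabelled. The rows say concurrent and define it, the plots say peak, and a strict table beside a sensitive plot is a reasonable pairing. That stands: this is not a contradiction in the plan. It does not remove the gap, because the only listing aimed at these patients is tied to the narrower definition, so the wider screen produces points that no targeted output resolves.

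Four stronger readings are tempting, and the SAP does not support them.
- **That any patient whose bilirubin rises after the transaminase is lost.** Patient A shows otherwise. Only patients with no qualifying date are affected.
- **That such patients go unreported.** They are counted in the separate ALT, AST and TBILI rows and enter the CTCAE shift tables. Their values are in the Section 6.6.5.2 listing. What is missing is the combined label and the targeted listing.
- **That the DLT criterion in Section 3.1 conflicts with the same-date rule.** It asks for a transaminase rise associated with raised bilirubin, but it sets no time window and serves another purpose.
- **That losses reach 79% (L=10, k=7, s=14) or 50% (L=21, k=7, s=28).** Those figures, 1 − 3/14 and 1 − 14/28, blame the rule for rises that were never sampled.

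Repeat testing would also shrink the loss. Section 3.1 asks for abnormal tests without associated clinical abnormalities to be repeated, in the DLT setting, and Section 5.2.9 generally includes unscheduled data. Finally, no decision rule in Section 5.1.2 uses this count, so the SAP gives no ground for saying that one missed case would change a trial conclusion.

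**Conclusion.** The gap follows directly from the wording of Section 6.6.5.1: a patient who meets both thresholds, but never on one date, is in the eDISH quadrant and in neither the combined rows nor the dedicated listing. The number of patients affected cannot be derived from the SAP. The range of none to 70% rests wholly on assumed values of L, k and s and on a fixed draw schedule without repeats, so it shows only that the loss could be material. Not every quadrant-only patient is a missed case, since unrelated peaks also land there. The change is worth making as a secondary safety-reporting improvement. It does not touch the primary endpoints or any decision rule.

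**What to change.** In Section 6.6.5.1:
- Keep the same-date rows unchanged as the strict subset.
- Add one row counting patients with peak (ALT or AST) at 3×ULN or more and peak TBILI at 2×ULN or more during the on-treatment period. Alternatively, require the two elevations to fall within a time window that the sponsor states and justifies.
- Extend the dedicated listing to all patients in the upper-right quadrant of either eDISH plot, showing dates, ALP and the days between the elevations, so that a reader can set aside unrelated ones. This also brings in quadrant patients with ALP above 2×ULN, such as patient E.

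The cost is SAP wording, one table row and a somewhat longer listing, using peaks already derived for the plots. The downside is that some listed patients will have unrelated elevations or hepatic progression.

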#### **Parameters with NCI-CTC grades available:**

The laboratory toxicities will be tabulated using descriptive statistics (number of patients and percentages) during the on-treatment period. The denominator to calculate percentages for each laboratory parameter is the number of patients evaluable for CTCAE grading (ie those patients for whom a Grade 0, 1, 2, 3 or 4 can be derived).

- The shift table will summarize baseline CTCAE grade versus the worst on-treatment CTCAE grade. The highest CTCAE grade during the on-treatment period is considered as the worst grade for the summary.
- The number and percentage of patients with newly occurring or worsening laboratory abnormalities during the on-treatment period will be summarized by worst grade on-treatment (Grade 1, 2, 3, 4, Grade 3/4 and any grade (Grades 1-4)).

The above analyses apply to hematology and chemistry evaluations which can be graded per CTCAE, ie:

- Hematology:  
Hemoglobin (HB), Leukocytes (white blood cell decreased), Lymphocytes (lymphocyte count increased/decreased), Neutrophils / Absolute Neutrophils Count (ANC) (neutrophil count decreased), Platelet Count (PLT) (platelet count decreased).
- Serum Chemistry:  
Albumin (hypoalbuminemia), Alkaline Phosphatase (alkaline phosphatase increased), Alanine Aminotransferase (ALT) (ALT increased), Amylase (serum amylase increased), Aspartate Aminotransferase (AST) (AST increased), Total Bilirubin (blood bilirubin increased), Creatinine (creatinine increased), Creatine Kinase (CPK increased), Potassium (hypokalemia/ hyperkalemia), Sodium (hyponatremia/ hypernatremia), Magnesium (hypomagnesemia/hypermagnesemia), Calcium (hypocalcemia/ hypercalcemia), Glucose (hypoglycemia/hyperglycemia), Gamma Glutamyl Transferase (GGT) (GGT increased), Lipase (lipase increased), Phosphates (hypophosphatemia).

